# **PROTOCOL SUMMARY**

Title:	An Open-Label, First-in-Human, Study Evaluating the Safety, Tolerability, and Efficacy of VC-02 ™ Combination Product in Subjects with Type 1 Diabetes Mellitus and Hypoglycemia Unawareness
Phase:	1/2
Population:	Subjects with type 1 diabetes mellitus (T1DM) and hypoglycemia unawareness (HU) will be enrolled into this first-in-human (FIH) clinical trial
	Cohort 1: At least three (3) subjects, but up to 15 total
	Cohort 2: Up to 60 subjects enrolled
	Total enrollment may be approximately 75 subjects
Number of Sites:	Approximately ten (10)
Study Duration:	The total duration of the trial is estimated to be up to 66 months:
	• Up to 42 months to complete enrollment of both cohorts
	• An additional 24 months from the time the last subject is enrolled in Cohort 2 until the last subject last visit
Subject Participation Duration:	Including Screening, Treatment, and Follow-up Visits, each subject's duration of participation is estimated as 110 weeks total (approximately two years).
	After all VC-02 units have been explanted, each subject will be required to be followed in a separate, long-term, follow-up study.
Description of Agent or Intervention:	ViaCyte has developed the VC-02 combination product, which is intended to control blood glucose in a more physiologic, sensitive, and homeostatic manner than the various forms of injectable insulin and pump therapies currently available. VC-02 combination product is comprised of two distinct components: (1) PEC-01 pancreatic endoderm cells derived from human embryonic stem cells (hESC) and (2) a durable, removable, Delivery Device (DD) designed to deliver and retain cells at the local implant site. Following subcutaneous implantation in anatomical locations
	involving the trunk or extremities, the VC-02 units are expected to vascularize adequately and the PEC-01 cells are expected to

differentiate into mature glucose-responsive, insulin-producing cells, capable of secreting insulin in response to serum glucose concentration.

Subjects may be implanted with VC-02-300 combination product for dose-finding, and smaller VC-02-20 combination product as sentinel units; these are smaller units that will be explanted at various time points and examined ex vivo.

An immunosuppression regimen will be used to facilitate the engraftment and long-term function of implanted VC-02 units. The overall regimen may vary between subjects but may include the use of basiliximab, anti-thymocyte globulin (ATG), etanercept, sirolimus, tacrolimus, steroids and/or mycophenolate mofetil (MMF). Additional medications can be prescribed by the Investigator to increase the safety and efficacy potential of the product after consultation with the Sponsor.

Study Design:This will be an open-label, FIH, clinical trial in subjects with
T1DM and HU.

Two cohorts are planned for enrollment in this trial:

Cohort 1 – Initial Safety and Tolerability: Up to 15 subjects may be implanted with up to two (2) VC-02-300 units and up to six (6) VC-02 sentinels at one (1) or more clinical sites. If no VC-02-300 units are implanted in a subject, up to ten (10) VC-02 sentinels may instead be implanted. Sentinel units may be explanted at varying time points post-implant to assess the status of cell viability and differentiation, vascularization, and host response. At a minimum, the first three (3) subjects in Cohort 1 will be enrolled sequentially in order to assess safety and tolerability data at Week 2 before implanting the next subject. If no serious, treatment-related adverse events (AEs) are observed with the first three (3) subjects after each has reached Week 2, subsequent Cohort 1 enrollment may be performed in parallel. Total duration of treatment (implantation) may be up to two (2) years for each Cohort 1 subject, with the last unit explanted at Month 24. Cohort 1 subjects will complete a total of 18 study visits.

After a minimum of three (3) subjects have been enrolled in Cohort 1 and have completed thru Week 4, the Data Safety Monitoring Board (DSMB) will review the cumulative Cohort 1 data for safety, tolerability, and proof of mechanism.

 $\underline{Cohort 2} - Up$  to 60 subjects will be implanted in cadres and will test a particular device configuration and/or implant strategy.

Based on information obtained from subject explants within a
given cadre, the need for an alternate device configuration and/or
surgical implant technique (e.g., pharmacological intervention,
implant site, etc.) may be identified in order to improve
engraftment and cell survival outcomes. These changes will be
implemented prior to the next cadre of subjects commencing
implantation to drive VC-02 engraftment optimization.
Cohort 2 subjects will be implanted with up to twelve (12) units.

Of the twelve implanted units, no more than ten (10) will be VC-02-300 and the remainder will be VC-02-20 units. For example, if ten (10) VC-02-300 units are implanted in a subject, two (2) VC-02 sentinels may be implanted. Cohort 2 enrollment will be competitive across approximately ten (10) sites. Sentinel units may also be explanted at various time points post-implant.

Total duration of treatment may be up to two (2) years for each Cohort 2 subject, with the last unit explanted at Month 24. Cohort 2 subjects will complete a total of up to 18 study visits.

Study Objectives:Objectives:This trial will test whether VC-02 combination
product can be implanted and maintained with safety,
tolerability and efficacy for up to two years. There are two
cohorts in this FIH trial with the following study objectives.

Cohort 1 study objectives:

- Assess the local and systemic safety and tolerability of VC-02 combination product when implanted into subjects with T1DM and HU.
- Assess histological proof of mechanism for VC-02 combination product (e.g., cell survival and differentiation to beta cells).

Cohort 2 study objectives:

- Evaluate the clinical efficacy and further assess safety and tolerability of VC-02 combination product from implantation to Month 24.
- Explore effects of weight, gender, BMI, or other potentially interacting factors on the responsiveness of the subjects to the experimental intervention.

Exploratory objectives:

• Optimize the recommended surgical implantation procedure, anatomical location, and perioperative care for VC-02.

18 MAY 2020Assess the effects of the host immune response to implanted VC-02 unitse primary endpoints vary between the two (2) cohorts and elude safety, tolerability, and efficacy.Cohort 1: Targeted safety and tolerability profile inclusive of:
VC-02 units e primary endpoints vary between the two (2) cohorts and clude safety, tolerability, and efficacy. Cohort 1 : Targeted safety and tolerability profile inclusive
clude safety, tolerability, and efficacy. Cohort 1 : Targeted safety and tolerability profile inclusive

 
The incidence of AEs with causality related to VC- 02 combination product, the surgical procedures required for VC-02 administration, and the immunosuppressive drug regimen.
 

• The incidence of off-target growth as evidenced by implanted VC-02 units via lumen ultrasound measurements, or by histological examination of explants.
• The incidence of immune sensitization defined by presence of donor anti-HLA antibodies absent prior to implant.

 
Implant tolerability assessments (e.g., fever, erythema, pain, tenderness, induration) for up to four hours post-implantation and at subsequent visits.
 

Cohort 2 : Change from baseline to Week 26 in C-peptide AUC 0-4h following a Mixed Meal Tolerance Test (MMTT)
fety and Tolerability: Comprehensive profile of VC-02 mbination product implanted for up to two years as measured :
All reported AEs
The incidence of immune sensitization defined by presence of donor anti-HLA antibodies absent prior to implant
Implant tolerability assessments (e.g., fever, erythema, pain, tenderness, induration) for up to four hours post-implantation and at subsequent visits
The incidence of subjects requiring a premature explant due to safety, tolerability, or malfunction issues
ficacy:
Change from baseline to Weeks 16, 26, 39, 52, 78, and 104 in average daily insulin dose in the seven days preceding the Clinic Visit

	• Percent of subjects who achieve a 50% reduction in average weekly exogenous insulin dose from baseline to Weeks 16, 20, 26, 39, 52, 78, and 104
	• Percent of subjects who achieve exogenous insulin independence; of those subjects achieving insulin independence, the percent achieving HbA1c <7.0%
	
 
Percent of time spent with blood glucose values at various cut points (e.g., <54 mg/dL, ≥54 to <70 mg/dL, ≥70 mg/dL to ≤180 mg/dL, and >180 mg/dL) as measured by each subject's continuous glucose monitoring (CGM) device
 

	
 
Change from baseline to Weeks 16, 26, 39, 52, 78, and 104 in time-in-euglycemic range (≥70 mg/dL to ≤180 mg/dL), time-in-hypoglycemic ranges (<54 mg/dL and ≥54 to <70 mg/dL), and time-in-hyperglycemic ranges (>180 mg/dL) as measured by each subject's CGM
 

Exploratory Endpoint:	Histological results of explanted units and any associated tissue capsule as evaluated for cell viability, vascularization, immune response, and/or cell maturation and differentiation.
Inclusion Criteria:	• Signed and dated informed consent form
	• Men and non-pregnant women of 18-65 years of age
	• Diagnosis of T1DM for a minimum of five (5) years
	• At least one severe hypoglycemic event, or for patients with CGMs, documentation of a low blood glucose value <54 mg/dL (<3.0 mmol/L), in the previous 12 months
	• Documented hypoglycemia unawareness (Clarke score ≥4) or significant glycemic lability as assessed by the Investigator
	• Stable, optimized diabetic regimen for at least 3 months
	• Insulin dosage at screening <1 unit/kg/day
	• Willing to use a provided CGM System
	• Willing and able to comply with daily entries on a study diary
	• All male subjects and female subjects of childbearing potential must practice effective contraception during the study and be willing and able to continue contraception until final explant. For further details of contraceptive requirements for this study, please refer to Section 5.4.5

ViaCyte Inc., Confidential	Amendment #9 – Version 8.0
Protocol #VC02-101	18 MAY 2020
Exclusion Criteria:	• A detectable stimulated serum C-peptide at any time-point during the Screening period, defined as >0.2 ng/mL (>0.0667 nmol/L)
	• Use of any oral diabetes-specific medication
	• Medical history of islet cell, kidney, and/or pancreas transplant
	• Occurrence of six or more severe, unexplained hypoglycemic events within six months of enrollment
	• Uncontrolled or untreated thyroid disease or adrenal insufficiency
	• Known causes of diabetes other than T1DM
	• Diabetic complications such as severe kidney disease or renal dysfunction, proliferative retinopathy, diabetic foot ulcers, amputations attributable to diabetes, and/or severe peripheral neuropathy
	• Non-compliance with current anti-diabetic regimen
	• Hemoglobin A1C level of $\geq 10.0\%$
	• Significant skin conditions involving the area(s) targeted for implantation
	Alcohol abuse
	• Positive urine drug screen for substances of abuse at screening or enrollment visit, medical marijuana use may be allowed by the PI after consultation with the Medical Monitor and/or Sponsor
	• Prior history of malignancy with the exception of:
	
 
Basal cell carcinoma of the skin;
 

	
 
Squamous cell carcinoma of the skin that has been recurrence free for ≥five years;
 

	$\circ$ Appropriately treated in situ carcinoma of the cervix
	• Known allergies to portions of the cellular excipients used as cell preservation solution or the PEC-01 manufacturing process (i.e., bovine, porcine allergies)

- History of severe asthma or COPD •
- BMI  $\geq$  32 kg/m2 or <18 kg/m2 at screening •

- Active hepatobiliary disease or an AST or ALT >1.5 x ULN at screening or a total bilirubin >1.5 x ULN unless the subject has a history of Gilbert's disease
- Active infection or known history of Hepatitis B or C or HIV
- Evidence of previous TB infection (including BCG vaccination or positive PPD)
- Negative serostatus for Epstein-Barr virus
- Other abnormal labs at screening:
  - o Platelets <100,000
  - $\circ$  Hgb <12 g/dL (males) or <11 g/dL (females)
  - Fasting triglycerides >500 mg/dL
  - Estimated Glomerular Filtration Rate (GFR)
     <60 mL/min/1.73 m2 (using MDRD calculator)

- Clinical lab value outside normal range, unless deemed as not clinically significant by the Investigator and Sponsor
- Sustained hypertension defined as average systolic ≥160 mmHg or diastolic ≥90 mmHg at screening
- 12-lead ECG findings demonstrating:
  - QTc>450 msec for males or >470 msec for females at screening
  - Any other abnormality deemed clinically significant requiring further clinical evaluation by the Investigator
- Any history of unstable angina or Class 3 or 4 CHF, or any of the following diagnoses/conditions or procedures within the past year: stroke, myocardial infarction, life-threatening arrhythmia, major cardiovascular procedure (e.g., angioplasty, planned angioplasty, or carotid endarterectomy), or any other clinically significant cardiovascular disease diagnosis or procedure
- History of coagulopathy
- Participation in a study of an investigational drug, device, or graft within five half-lives of the experimental agent or 30 days prior to enrollment in this study, whichever is longer
- Planned surgery in the general location of the implanted units (i.e., back and/or flank, arms, legs, abdomen, etc.) at any time during study participation

Statistical Considerations	
 
Sample Sizes – Cohorts 1 and Cohort 2
 
Sample size in Cohort 1 was empirically derived, based upon safety considerations and data accumulated from previously performed ViaCyte clinical trials. A sample size of up to 15 subjects should allow for adequate assessment of Cohort 1 study objectives.
 

	• A sample size of 60 subjects in Cohort 2 will enable staggered enrollment of cadres of subjects allowing for testing of alternate device configurations and/or surgical implant technique (e.g., pharmacological intervention, implant site, etc.) in order to improve engraftment and cell survival outcomes. This approach will drive VC-02 engraftment optimization.
	Sample Size – Primary Efficacy Endpoint
	
 
Once the optimized device configuration and surgical implant technique is determined, a sample size of 40 subjects implanted
 
If the minimal level of detection for C-peptide is 0.20 ng/mL, this would give an AUC of 0.8 ng x hour/mL for the 4-hour MMTT. A sample size of 40 subjects
 
For the 2-hour MMTT, a sample size of 40 subjects
 

	Analysis Populations
	• The Full Analysis Set (FAS) is defined as Cohort 2 subjects enrolled into the study and who received implantation of at least one VC-02 unit on Study Day 1. All efficacy summaries/analyses will be performed on the FAS. Subjects will be summarized by treatment group.
	• The Safety Analysis Set (SAS) will include all Cohort 1

• The Safety Analysis Set (SAS) will include all Cohort 1 and Cohort 2 subjects enrolled into the study and in whom an implant surgery was attempted, regardless if any VC-02 units were actually implanted.

Primary Safety

- The SAS will be used for the primary safety summarizations. Adverse events and SAEs will be summarized by system organ class (SOC), by severity, and by relationship. This will be done by treatment group and overall.
- The summarization of AEs will focus on only those events that are TEAEs, but the AE listings will include all reported AEs regardless of when they started.
- Other safety data, such as vital signs and clinical laboratory data will be summarized by study visit and treatment group. Where appropriate, change from baseline in safety data will also be summarized in a similar manner.
- The number of subjects undergoing a premature VC-02-300 unit explant will be provided in a listing which includes the reason for explantation.

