## **3. STUDY DESIGN**

This will be an open-label, FIH, clinical trial in subjects with T1DM and HU. Two cohorts are planned for enrollment in this trial, with enrollment of Cohort 1 occurring prior to enrollment of Cohort 2.

All enrolled subjects in Cohort 1 will have up to ten VC-02 units and in Cohort 2 will have up to eleven VC-02 units implanted

s deemed appropriate by the	
Investigator and/or Surgeon after consultation with the Sponsor. Documentation of the implant	
plan for a subject will be provided to the Investigator by the Sponsor.	

At the end of the treatment period for each subject, all remaining implanted units will be removed, and the subject will be required to participate in a separate, follow-up, non-interventional, observational study. The primary purpose of this additional study is to ensure there are no long-term safety issues associated with previous implantation with VC-02.

Each Cohort is described in further detail below.

# **3.1.** Cohort 1

Enrollment of Cohort 1 will occur first in this study at one (1) or more clinical sites. A minimum of 3 and up to 15 subjects may be enrolled in Cohort 1. Initially, up to ten (10) VC-02-20 units (sentinels) will be implanted in Cohort 1 subjects in order to maximize the amount of available histologic data. However, the first three (3) subjects enrolled in Cohort 1 will not be implanted with VC-02-300 units.

[figure not shown]
. After the first three

subjects are enrolled in Cohort 1, VC-02-300 units may then be implanted in subsequent subjects and the stimulated C-peptide levels will be monitored. These additional Cohort 1 subjects may be implanted with up to two (2) VC-02-300 units and up to six (6) VC-02 sentinels total. The decision as to the number of VC-02-300 units implanted in subsequent subjects will be data-driven and this number may be reduced. However, if no VC-02-300 units are implanted in these additional Cohort 1 subjects, up to ten (10) VC-02 sentinels may instead be implanted.

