The total duration of treatment (implantation) may be up to two (2) years for each Cohort 1 subject. Sentinels may be explanted at various time points post-implant to assess the status of cell viability and differentiation, vascularization, and the host response. The VC-02-300 unit(s) and all remaining sentinel units will be explanted at Visit 17/Week 104. Including the requirements of the screening period, Cohort 1 subjects will complete a total of 18 study visits spanning approximately 25 months as outlined in Table 1 – Schedule of Assessments. At a minimum, the first three (3) subjects in Cohort 1 will be enrolled sequentially in order to assess safety and tolerability data thru Week 2 before implanting the next subject. For example, data thru Week 2 from the first subject will be formally reviewed by the Sponsor prior to allowing the Investigator to implant the next subject. If a treatment-related SAE is observed within the first two weeks in the subject, the implantation of the next subject will be postponed until consultation between the Sponsor and Investigator has devised appropriate safeguards. Overall, if no treatment-related SAEs are observed with the first three (3) subjects after each has reached Week 4, additional Cohort 1 enrollment may then be performed in parallel.

A target minimum of three (3) evaluable subjects will be enrolled as part of Cohort 1, but up to 15 total subjects may be enrolled in Cohort 1 if the Sponsor and/or Data Safety Monitoring Board (DSMB) determine that additional subject data are necessary to properly evaluate the investigational product and/or the implantation procedure. After the minimum of three (3) subjects have been enrolled in Cohort 1 and have completed thru Week 4, the Sponsor then has the ability to initiate enrollment of Cohort 2 and request the DSMB to meet to review the cumulative Cohort 1 data for safety, tolerability, and proof of mechanism.

The DSMB will not meet regularly during Cohort 1 unless the Sponsor seeks an independent DSMB review based on Sponsor or Ethics Committee (EC) recommendations for managing AEs. The DSMB chair and/or the entire DSMB may receive regular updates as to the progress of the trial during Cohort 1.

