# 8.4. Data Safety Monitoring Board (DSMB)

An independent Data Safety Monitoring Board (DSMB) will meet at specified times throughout the study to review the accumulation of data. The DSMB will consist of at least 3 members, including a statistician. No Investigator involved in the trial or anyone connected to the Sponsor or participating vendors such as a CRO may be a member of the DSMB. Based on the review of the study data, the DSMB may make recommendations regarding the conduct of the study. These may include, but are not limited to, amending safety monitoring procedures, modifying the protocol or consent, terminating the study, or continuing the study as designed. The discussions and decisions of the DSMB will be summarized in written minutes and provided to the Sponsor. When necessary, summary DSMB minutes may be distributed to participating sites for submission to Ethics Committees. A separate DSMB Charter will direct the activities of the Board.

The approximate timing of DSMB meetings are noted below:

- After a minimum of three (3) subjects from Cohort 1 have reached the Week 4 clinic visit and the results are available, the Sponsor then has the ability to request the DSMB to meet. The available cumulative data collected in all subjects from Cohort 1 up until that time will be evaluated by the DSMB. Based on review of the available data, the DSMB will make a recommendation on the enrollment of Cohort 2. The DSMB will not meet regularly during Cohort 1 unless there is a related AE that requires an independent DSMB review.
- Quarterly during the first year of Cohort 2, and thereafter every three (3) to six (6) months until the last visit of the last Cohort 2 subject has occurred.

Additional meetings of the DSMB may be scheduled based on data review needs or by request.

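### The Protocol Summary opens parallel Cohort 1 enrolment at Week 2, while Section 3.1 and the SAP set Week 4 for the same gate

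*Protocol*

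**What the plan says.** Three places state when Cohort 1 may move from sequential to parallel enrolment.

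- **Protocol Summary, Study Design:** provided the first three subjects have had no serious treatment-related AE, "after each has reached Week 2, subsequent Cohort 1 enrollment may be performed in parallel".
- **Protocol Section 3.1:** provided the same three subjects have had no treatment-related SAE, "after each has reached Week 4, additional Cohort 1 enrollment may then be performed in parallel".
- **SAP Section 3.2.3:** restates the Section 3.1 rule, with Week 4.

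Two neighbouring rules are separate and not in dispute. The first is the subject-to-subject stagger, on which all three texts agree: at least the first three subjects are enrolled one after another so as to assess "safety and tolerability data thru Week 2 before implanting the next subject". Section 3.1 adds, by way of example, that the first subject's data are "formally reviewed by the Sponsor prior to allowing the Investigator to implant the next subject". The second is the DSMB review that informs the recommendation on Cohort 2, which Protocol Section 8.4 places as follows: "After a minimum of three (3) subjects from Cohort 1 have reached the Week 4 clinic visit and the results are available".

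**The concern.** The gate ends one-at-a-time implantation of a first-in-human product given with immunosuppression, and the protocol gives it two different values. Someone working from the Summary could release overlapping implants at a point where someone working from Section 3.1 would still be waiting.

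Neither version makes the gate wait for the DSMB. Section 3.1 says: "The DSMB will not meet regularly during Cohort 1 unless the Sponsor seeks an independent DSMB review". The stated week is therefore the protocol's minimum follow-up before implants may overlap. What is at stake is some days of clinical observation, chiefly in the third subject. Neither version requires laboratory results to be in hand, so the argument concerns length of observation only.

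**Working it through.** **Is it the same gate?** The texts match on every element except the week.

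| Element | Protocol Summary | Section 3.1 and SAP 3.2.3 |
|---|---|---|
| Subjects | first three in Cohort 1 | first three in Cohort 1 |
| Condition | no serious treatment-related AE | no treatment-related SAE |
| Release | parallel Cohort 1 enrolment | parallel Cohort 1 enrolment |
| Timing | each at Week 2 | each at Week 4 |

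The Summary's Week 2 cannot be the stagger, because the Summary states the stagger in the sentence before. It cannot be the DSMB rule either, since that is stated separately and uses Week 4.

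**Inputs.** From the visit windows in Protocol Table 1, in days after a subject's own implant:

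- Week 2 = 14 ± 2, so 12 to 16
- Week 4 = 28 ± 3, so 25 to 31

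Assumption: each next implant falls on the previous subject's Week 2 visit, with no extra time for the Sponsor's review. The documents give no review time. Added time would lengthen follow-up of subjects 1 and 2 but would not change the third subject's gap.

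**Nominal schedule.** Implants fall at weeks 0, 2 and 4.

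- Summary gate: 4 + 2 = week 6. Follow-up of subjects 1/2/3 is 6/4/2 weeks, or 42 + 28 + 14 = 84 subject-days.
- Section 3.1 gate: 4 + 4 = week 8. Follow-up is 8/6/4 weeks, or 56 + 42 + 28 = 126 subject-days.
- Difference: 14 days.

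**Across the windows.**

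- Summary gate: 12 + 12 + 12 = day 36 to 16 + 16 + 16 = day 48.
- Section 3.1 gate: 12 + 12 + 25 = day 49 to 16 + 16 + 31 = day 63. The third subject always sets it: the second subject's Week 4 visit falls at most 31 days after that subject's own implant, whereas the third subject's falls at least 12 + 25 = 37 days after it.
- Third subject's gap: 25 − 16 = 9 days to 31 − 12 = 19 days.
- Second subject at the Summary gate: 12 + 12 = 24 to 16 + 16 = 32 days of follow-up, so that subject's Week 4 visit is outstanding by at most 31 − 24 = 7 days.
- First subject at the Summary gate: 36 to 48 days, always past Week 4.

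**What Section 3.1 already allows in the interval.** A fourth subject implanted sequentially after the third subject's Week 2 review appears to be permitted by all three texts. A fifth would come at 14 + 14 = 28 days after the third implant, which is the third subject's nominal Week 4. At nominal visits the practical contrast is therefore one sequential implant against overlapping ones.

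**The case against.** The case for giving this little weight is good, and most of it stands.

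- **Use of VC-02-300 units.** A reader might infer that the earlier gate brings forward the first larger units, because "the first three (3) subjects enrolled in Cohort 1 will not be implanted with VC-02-300 units". The documents do not support that. Section 3.1 ties their release to the first three subjects being enrolled, after which "VC-02-300 units may then be implanted in subsequent subjects"; SAP Section 3.2.3 adds only that initial safety and tolerability be confirmed. A permitted sequential fourth subject could receive the first such units under either version. The gate delays overlap, not first exposure.
- **Number of subjects.** A reader might also infer that 15 − 3 = 12 subjects could be implanted at once. That is the remaining Cohort 1 cap, not a forecast. The Sponsor sets each subject's implant plan (Protocol Section 5.1.4), ships product labelled for a designated patient (5.1.2) and is contacted at screening to schedule supply (6.1). A site could not open the gate alone.
- **Other safeguards.** SAEs must be reported to the Sponsor within 24 hours (8.2.2), the stopping rules call for an ad hoc DSMB meeting (8.5), and close communication is required during Cohort 1 (10.3.1).
- **Possibly moot.** The SAP revision log cites safety deliverables and interim safety summaries, so subjects had been treated by then and the gate may well have been passed. No enrolment dates are given.
- **Precedence.** Some pages are absent from the public copy, so one can say only that no visible text settles which section governs. The SAP restates the protocol rule and is not an independent source.

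These points limit the consequence. None of them reconciles the two sentences, both of which are current text.

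**Conclusion.** The inconsistency is real: one first-in-human decision threshold has two values in the same protocol. It is minor, and it is a conflict between synopsis and body rather than a flawed design choice. Its whole effect is on when overlapping Cohort 1 implants may begin: 14 days earlier at nominal visits under the Summary, 9 to 19 days across the windows, borne mainly by the third subject. The third-subject gap depends only on the visit windows. The follow-up figures for subjects 1 and 2 also assume no added review time and are minimums in that respect.

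Confidence is high for the text mismatch. The documents do not support a larger safety claim: they show neither that the Summary's timing was ever applied nor that any subject was implanted too early.

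**What to change.** In the parallel-enrolment sentence of the Protocol Summary, change Week 2 to Week 4. Leave the Week 2 subject-to-subject stagger, Section 3.1 and SAP Section 3.2.3 as they are. This keeps the longer observation already stated in the protocol body.

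The cost is one word at the next amendment. If the gate is still ahead, parallel enrolment starts about two weeks later than the Summary would allow (9 to 19 days across the windows). If it has been passed, the change aligns the text and alters no conduct. Checking which threshold was actually used would then be an audit step, separate from this correction, and a single sequential fourth implant should not be flagged.
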